#### [Integration with patient care](#)

Throughout the program, patients will be instructed to follow their normal care plan as directed by their medical providers and as consistent with ADA 2017 standard-of-care guidelines. This includes taking medications as prescribed; engaging in physical activity—especially walking after meals; eating a diet that optimizes glucose control through food choice and timing; responding to hypoglycemia symptoms with a fingerstick and consuming a pre-determined amount of glucose; and monitoring emotional wellness. By providing a continuous graph of each participant's glucose, the CGM system illustrates how the above-described glucose management behaviors impact the participant's glucose.

Should patients in the course of the program experience any health problems associated with the use of their CGM devices, they will be directed to contact the study doctor's CRC. The CRC will assess the severity and relatedness of the event and arrange for appropriate care. Should patients mention a potential study-related health concern to their coach, the coach will actively work to assure the patient speaks with the study doctor, either through a warm transfer or callback.

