#### **Training of site staff**

Site staff at Machuca Family Medicine will be oriented to the study and equipped to conduct recruitment and enrollment as needed. The CRC at the study site has previous experience in conducting clinical research specifically with Dexcom CGM devices. The CRC will be trained to instruct patients in using the investigational device. The CRC will also be trained in the specific protocol to assess and document adverse events.

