- There are no expected electrical safety risks as the device has passed the electrical safety tests as per EN45502-1 and EN60601;

- If the subject feels any discomfort during the course of the study, he/she will be able to remove the device immediately (the device is not permanent);
- The device is being used to complement, not replace, self-monitoring of blood glucose meter information, and readings are not intended to be used alone to make diabetes self-management decisions. As with the currently approved device and per intended use of similar technologies, subjects in the study will be instructed not to use the device for diabetes therapy or management;
- Subjects will be instructed to monitor their blood glucose levels as per their usual practice.

Adverse events (AE) associated with the use of the device include pruritus (severe itchiness present 48 hours after removal), erythema (reddening of the skin present 48 hours after removal), and inflammation (swelling and pain, defined as 8 or greater on a 10 point scale 48 hours after removal) where the adhesive touches the skin; local infection at insertion site; and shooting pain located at the site of the sensor (defined as 8 or greater on a 10 point scale). Rarely, the sensor wire will fracture when the sensor is being inserted, worn, or removed. If a sensor breaks and no portion of it is visible above the skin, the participant will be instructed to not remove it and seek medical care from the study doctor and/or his staff.

No serious adverse events (SAE) are expected as a result of participation in this minimal risk study. However, AE and SAE will be monitored in the following ways:

- Participants in the study will be instructed to call the study doctor's clinical research coordinator to report all AE and SAE related to the use of the study devices. The study doctor and/or his staff will assess the severity of any health problems associated with the device, and if needed, see the patient at the study clinic to assure appropriate care.
- Study coaches will listen for any reports of AE or SAE in the course of their communications with participants, and will connect reporting patients with the study doctor's clinical research coordinator so events can be assessed and documented and patients can receive care, if needed.

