## 22. Appendix B

### Adverse Events Severity and Relatedness Questions

May 2017

When patients share a complaint, program coaches will identify the complaint in the Anticipated Complaints Guidebook. Based on the complaint type, coaches will then ask questions to determine:

1. Severity of the complaint (e.g., Mild, Moderate, or Severe), and
2. Relatedness of the complaint to the use of program devices (e.g., Not Related, Probably Not Related, Possibly Related, and Probably Related)

Coaches will document answers in the templates provided, including the Adverse Event document.

If the complaint falls in any of the severity categories highlighted in red, the coach will make a “warm transfer” to the study doctor and/or his staff so that the patient can be scheduled for an ancillary appointment.

If the complaint is an emergency, patients will be instructed to call 911.

If a patient has a complaint that is not listed in the Anticipated Complaints Guidebook, the coach can “warm transfer” the patient to the study clinic for guidance. The coach will document as much as possible in Adverse Event document. Follow up with the clinic will determine severity and relatedness.

Coaches will contact the PI when situations arise that are not covered in the Anticipated Complaints Guidebook.

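### For a listed complaint reported to a coach, the protocol gives two conflicting rules on who assesses severity and relatedness and when the patient is referred

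*Protocol*

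**What the plan says.** Section 6, Integration with patient care, covers patients with health problems linked to the CGM device: "The CRC will assess the severity and relatedness of the event and arrange for appropriate care". When a patient mentions a potential study-related concern to a coach, "the coach will actively work to assure the patient speaks with the study doctor". No severity threshold is attached. Under Training of site staff, "The CRC will also be trained in the specific protocol to assess and document adverse events".

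Section 9 gives three reporting routes. For participants' own reports, "The study doctor and/or his staff will assess the severity of any health problems associated with the device". For the coach route, "Study coaches will listen for any reports of AE or SAE in the course of their communications with participants", and they connect the patient with the CRC "so events can be assessed and documented and patients can receive care, if needed". For reports that arrive through the manufacturer, the CRC follows up and assesses both severity and relatedness. Section 9 also points to an appendix with AE assessment guidance for coaches.

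Appendix B (Section 22) works differently. The coach finds the complaint in a guidebook, asks scripted questions that determine severity and relatedness, and enters the answers in templates that include the Adverse Event document. Transfer to the study doctor or his staff is conditional: "If the complaint falls in any of the severity categories highlighted in red". Only for a complaint missing from the guidebook does follow-up with the clinic determine severity and relatedness.

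**The concern.** Severity, relatedness and the decision that something is an AE are the content of the study's safety table. In the body of the protocol they belong to the CRC, or to the study doctor and his staff for severity. In Appendix B they follow from a coach's script that converts a patient's score into a grade, or into a decision not to record an AE, and converts sensor location into a relatedness category.

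If both rules are in force, the same complaint can be classified and referred differently according to which section a staff member follows. The device is investigational, and Section 9 has the sponsor-investigator report AEs to the IRB, the manufacturer and the FDA. The assessor of record should therefore not be in doubt.

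**Working it through.** The plan gives no figure on this point, so the check sets the stated rules side by side.

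**Step 1: assessor and referral by route.**

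| Route | Severity | Relatedness | Referral |
|---|---|---|---|
| Patient contacts the clinic (Sections 6, 9) | CRC, or study doctor and/or staff | CRC | Already at the clinic |
| Report via the manufacturer (Section 9) | CRC | CRC | CRC follows up |
| Report to a coach (Sections 6, 9) | CRC, or study doctor and/or staff | CRC | No severity threshold |
| Report to a coach, unlisted complaint (Appendix B) | Clinic | Clinic | Coach can transfer |
| Report to a coach, listed complaint (Appendix B) | Coach | Coach | Red-marked grades only |

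The CRC is described as the study doctor's coordinator, so the first two rows are compatible. On who assesses, the unlisted complaint also agrees with the body. The conflict lies between the third row and the last.

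**Step 2: can it be read as triage?** Triage would need a step in which the CRC confirms or overrides the coach's grade. None is visible for complaints that are not transferred, or for those the script says not to record as an AE. Appendix B gives the determination to the clinic only for unlisted complaints, which suggests that for listed ones the coach's determination stands. The coach training described in Section 6 does not mention AE assessment; the CRC's does.

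**Step 3: one complaint traced through both rules.** A sensor breaks and no part shows above the skin.
- Section 9: the participant is told not to remove it and to seek care from the study doctor and/or his staff. Section 12 also makes its minimal-risk statement for a retained sensor depend on a physician's check.
- Appendix B, Detached/Broken Sensor Wire: the coach asks whether the wire is visible, and a negative answer ends the script. No grade is assigned, so no severity category can trigger transfer.

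**Step 4: which way would counts move?** Section 9 defines device AEs narrowly: severe itch 48 hours after removal, swelling and pain of 8 or more 48 hours after removal, and shooting pain of 8 or more. Appendix B counts an AE from 3 for insertion-site pain and from 6 for itch and swelling, and it adds bruising and bleeding. For most complaint types it captures more. Redness can go the other way: Section 9 counts redness still present at 48 hours with no score, while Appendix B leaves ratings of 1-5 unrecorded as AEs unless itch or pain is moderate.

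**Step 5: how often could it arise?** Appendix B scripts cover eight complaint types: redness or rash, itch, pain, swelling, bruising, bleeding, infection and broken wire. With 100 participants, one coach call a week and 10 weeks of CGM, 100 × 10 = 1,000 calls would be scheduled during CGM wear. This assumes full enrolment and completion. It counts opportunities to report, not complaints.

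**The case against.** The best defence is that coach screening with clinic assessment is the intended design, and that Section 9's pointer to coach guidance shows it. The Appendix C reporting chart, of which only the heading is available here, may show where untransferred forms go. That is fair, and it means nobody can say from this text that a coach's grade is final. A chart would still leave the conflicting sentences in place, and none of them ranks the coach's determination against the CRC's.

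A reader might also infer several stronger things that the documents do not support:
- **That low-scored complaints leave no record.** Coaches document answers in templates, and Section 9 has AE-related conversations logged in call-management software and the Case Report Form. What the scripts withhold is classification as an AE.
- **That Section 9 sends every such complaint to the CRC.** Its coach route concerns AEs and SAEs as Section 9 defines them. The referral without a threshold rests more firmly on Section 6.
- **That AEs are undercounted.** Step 4 points in both directions.
- **That all Mild AEs escape CRC review.** The red marking did not survive extraction, which is no fault of the plan. The asterisks in the scripts should not be taken as a substitute for it.
- **That coaches are non-medical.** Their credentials are not stated.

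**Conclusion.** Wrong as written. For a listed complaint reported to a coach, Sections 6 and 9 and Appendix B prescribe different assessors and different referral rules. AE classification, grade, relatedness and referral can therefore depend on the section followed.

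The finding needs only that transfer is conditional in Appendix B and carries no severity threshold in the body; it does not depend on which grades are red. The supported harm is inconsistency. No number of affected events can be derived, and neither undercounting nor overcounting is shown. The broken-sensor case is the firmest instance, because the two instructions for the same event differ outright. The assumption throughout is that the unseen Appendix C chart and guidebook contain no sentence that settles precedence.

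**What to change.** 1. Reconcile Section 6 (Integration with patient care) and Section 9 with Appendix B on who assesses and when a coach refers.
2. Name one role as assessor of record for severity and relatedness, for every reporting route.
3. State in Appendix B that the scripted scores are coach intake and not the final assessment.
4. Route the coach-completed Adverse Event documents and templates to that assessor, including those the script says not to record as an AE.
5. Reconcile Section 9 with the Detached/Broken Sensor Wire script. Which instruction should apply is a clinical decision for the sponsor and investigators.

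The cost is revised wording, routing of forms that coaches already complete, and some added reading time for the CRC.

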#### Skin Redness or Rash – Severity Category

1. On a scale of 1 to 10, where 1 is very little, and 10 is severe, how would you rate the redness of your skin or rash?
  - If 1-5, do not record as AE, **unless itchiness and/or pain are moderate**
  - If 6-7, Mild AE
  - If 8-9, Moderate AE**
  - If 10, Severe AE**
2. Are you experiencing **pain or itchiness** where your skin is red or where you have a rash?
  - If no, stop.
  - If yes, on a scale of 1 to 10 where 1 is very little, and 10 is severe, how would you rate the **itchiness**?
    - If 1-5, do not record as AE
    - If 6-7, Mild AE
    - If 8-9, Moderate AE**
    - If 10, Severe AE**

- If yes, on a scale of 1 to 10 where 1 is very little, and 10 is severe, how would you rate the **pain**?
  - If 1-2, do not record as AE
  - If 3-5, Mild AE
  - If 6-8, Moderate AE**
  - If 9-10, Severe AE**

#### **Skin Redness or Rash – Relatedness Category**

1. Where is the location of the redness or rash?
  - If in the same location as the sensor on your skin, then Probably Related
  - If in a location where a sensor was within 2 days, then Possibly Related
  - If in a location where a sensor was 2+ days in the past, then Probably Not Related
  - If in a location where a sensor was never placed, then Not Related

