## Risks of CGM

When the wire-like sensor is deployed by the applicator, participants can expect a sensation similar to a needle insertion for a blood draw. Risks of CGM use include discomfort during sensor insertion, along with pain, inflammation, redness, swelling, minor bleeding and minor infection at the sensor insertion site. Participants might also experience these symptoms as a result of contact between the adhesive pad of the sensor and the skin. In rare cases, an infection can spread to other parts of the body.

Allergic reactions can develop in response to the sensor, the adhesive, and other parts of the CGM. If these symptoms occur, participants have the ability to remove the CGM at will and can anticipate that their symptoms will clear up within one week.

The sensor and/or applicator may fracture during use. If a sensor remains in the skin, there is minimal risk to the patient as long as a physician confirms there are no symptoms of infection or inflammation.

Patients will be advised that the investigational sensor, transmitter, and smartphone must be removed before Magnetic Resonance Imaging (MRI), Computed Tomography (CT) scan, or diathermy treatment. The device is MR Unsafe. Participants should not bring any portion of the device into the MR environment. The Dexcom IUO CGM System has not been tested during MRI or CT scans or with diathermy treatment. The magnetic fields and heat could damage the device, causing it to stop displaying glucose readings, display inaccurate glucose readings, or prevent alerts.

Patients will also be advised of CGM system warnings that may affect the proper operation of the device and/or the patient's safety. These warnings will be described in the informed consent and authorization form, and in the informational materials provided to patients when they receive their systems.

Patients will be provided with a phone number for Dexcom Customer Care and Technical Support that has been set up exclusively for patients participating in this study. Staff for this line will be well-qualified to address any potential questions and risks associated with the investigational device. Significant or serious health risks with CGM are not anticipated.

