#### **Skin Itchiness – Relatedness Category**

1. Where is the location of the itchiness?
  - If in the same location as the sensor on your skin, then Probably Related
  - If in a location where a sensor was within 2 days, then Possibly Related
  - If in a location where a sensor was 2+ days in the past, then Probably Not Related
  - If in a location where a sensor was never placed, then Not Related

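### The coach script labels itch or redness at a site used 2+ days ago Probably Not Related, although Section 9 describes device-associated itch and redness by their presence 48 hours after removal

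*Protocol*

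**What the plan says.** Section 9 (Assessment of Safety) lists the adverse events associated with use of the device. Two of them are "pruritus (severe itchiness present 48 hours after removal), erythema (reddening of the skin present 48 hours after removal"). A third is "inflammation (swelling and pain, defined as 8 or greater on a 10 point scale 48 hours after removal) where the adhesive touches the skin".

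Appendix B gives coaches a severity script and a relatedness script for each type of complaint. For redness or rash the only relatedness question is "Where is the location of the redness or rash", and for itchiness it is "Where is the location of the itchiness". A complaint at the current sensor site is Probably Related. For former sites the redness script reads "If in a location where a sensor was within 2 days, then Possibly Related" and then "If in a location where a sensor was 2+ days in the past, then Probably Not Related"; the itchiness script has the same two lines.

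On what happens to the answers, the opening of Appendix B says: "Coaches will document answers in the templates provided, including the Adverse Event document". In Section 12, on allergic reactions to the sensor or adhesive, Risks of CGM says "participants have the ability to remove the CGM at will and can anticipate that their symptoms will clear up within one week".

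**The concern.** The two places use the same cut-point in opposite directions. In Section 9, presence at 48 hours is part of the description of a device-associated event. In Appendix B, passing that point moves the label to Probably Not Related.

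At stake is how skin reactions to an investigational sensor are classified. For reactions reported late, the scripted label errs in one direction only, toward not related. Because the script asks for no onset date, its answers do not allow the label to be corrected afterwards.

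**Working it through.** No sample size or test is involved. The check sets the two rules side by side and counts how far the wording reaches.

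**Common time unit.** 48 hours / 24 = 2 days, so Section 9's time condition and the Appendix B cut-point coincide.

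**One reaction followed through both rules.** Take redness, or severe itch, that begins under the sensor and persists.

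| When the coach first rates it | Section 9 time condition | Appendix B label |
|---|---|---|
| Sensor still worn at the site | cannot yet be judged | Probably Related |
| Less than 48 hours after removal | cannot yet be judged | Possibly Related |
| Exactly 48 hours after removal | met | both former-site lines can be read to apply |
| More than 48 hours after removal, e.g. day 3 | met | Probably Not Related |

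The conflict lies in the last row, with an ambiguity in the row above it. Reactions rated earlier are unaffected. The last row is not a remote case: Risks of CGM allows up to one week for such symptoms to clear. That is an upper bound, and its starting day is not stated.

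**Can the wording be reconciled?** The 2+ days line does not say whether the interval runs to the rating or to the start of the complaint. If it ran to the start, a reaction that began under the sensor would not fall under it, and the two places would agree. That reading needs an onset date. I looked for one in every severity and relatedness script. The nearest questions are whether a bruise is growing and whether bleeding has stopped; neither gives an onset. The second reading therefore cannot be applied from the script's answers.

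**Reach of the wording in Appendix B.**
- Relatedness scripts: redness or rash, itchiness, pain or discomfort, swelling, bruising, bleeding, infection, broken sensor wire = 8.
- With the 2+ days line: all except broken sensor wire = 7.
- Asking for onset: 0 of 8.
- Of the 7: redness and itchiness (2) correspond directly to Section 9's 48-hour items. Pain and swelling (2) match loosely, because Section 9 combines them in one item and the scripts rate them separately. Bruising, bleeding and infection (3) have no 48-hour counterpart in Section 9 and are outside this point: 2 + 2 + 3 = 7.

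**Planned exposure.** Inputs: 100 participants (Section 7), 10 weeks of wear (Section 6, Program Length), 10-day sensor life (Section 6, Dexcom CGM System). Assuming full wear by everyone:
- 10 weeks × 7 days = 70 days
- 70 / 10 = 7 sensor sites per participant
- 7 × 100 = 700 sites

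Each site eventually passes the 2-day line. This counts sites, not reactions; how many would have a late-reported reaction is unknown.

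**The case against.** The strongest reply is that the coach's label is only intake. Section 9 says coaches who hear of an adverse event will connect the patient with the clinical research coordinator for assessment and documentation, and it does not limit this to unlisted complaints. Section 9 gives a similar follow-up for reports reaching the manufacturer's support line, Section 6 (Integration with patient care) has the coordinator assess severity and relatedness, and the site training text says the coordinator will be trained for it. The document nowhere says that the coach's label is final. This stands, and it is why no bias in the final record is claimed. It does not make the two rules agree: Appendix B has coaches determine relatedness and record their answers, and within that appendix determination by the clinic is stated only for complaints not in the guidebook. The visible text does not say which assessment prevails for listed complaints.

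Second, severe itch may be the very case that reaches the clinic. Transfer depends on severity categories highlighted in red, and a rating of 10 is the only itch category marked with asterisks. If the asterisks stand for the lost colour, which is an assumption, such a report is transferred. That is fair, and no loss of events or of care is claimed, since recording and transfer follow severity and not this label.

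Third, an onset date could be captured on forms not visible here: the adverse event template, the case report form, the guidebook, or the Appendix C chart. This also stands. The statement about onset is limited to the printed script, whose label is assigned from location alone whatever another form records.

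Fourth, it may be ambiguous wording more than a contradiction. The ambiguity is real, but the reading that removes the conflict needs information the script does not collect.

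Finally, relatedness is not among the study's stated aims or endpoints, and no rule maps the four levels to related or unrelated. That limits the consequence. It does not remove the mislabelling.

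**Conclusion.** The point holds and should be fixed. As printed, a reaction that begins under the sensor, persists and is first rated more than 48 hours after removal meets Section 9's time condition for a device-associated event and receives the label Probably Not Related. The conflict is direct for redness or rash and for itchiness, looser for insertion-site pain and swelling, and absent for the other scripts.

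The textual mismatch is certain. Its effect on the record of related adverse events cannot be derived from the document, and no rate is claimed. The conclusion rests on two things: the printed script being what coaches apply, and the 2 days being counted to the rating, which is the only way to apply the line from the script's answers. If the coordinator reassesses every report with onset in hand, the final record may be right even though the scripted label is wrong.

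**What to change.** Reconcile Section 9 with the relatedness scripts for redness or rash and itchiness, and bring the pain and swelling scripts into line.

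- Add a question on the date the complaint began.
- State the reference date from which the 2 days are counted, and make the two former-site lines exclusive at exactly 48 hours.
- Base the relatedness label on site plus onset relative to sensor wear, not on time since removal alone.
- Record persistence at 48 hours after removal as a separate field.
- If Appendix C does not already do so, say whether the coach's or the coordinator's assessment is the one of record for listed complaints.

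The cost is one extra scripted question and small edits to Appendix B, to the adverse event template if it lacks these fields, and to Section 9 if its wording is the side changed. The number of events classed as related may rise.
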